2.9.2 Secondary analyses

Principal component analyses and non-metric multidimensional scaling will be used to determine whether there is a distinct hospital-acquired NPR in hospitalised participants. Conditional logistic regression will be used to test for association between NPR composition and re-hospitalisation with pneumonia within a 3-month period, controlling for potential confounders including co-morbidities, nutritional status, duration of hospital admission and severity of pneumonia.

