1.3 Study Objectives

1.3.1 Broad Objective

To determine whether hospital admission and antibiotic treatment for pneumonia generate a persistent hospital-acquired nasopharyngeal resistome in Malawian children, and whether this is associated with adverse health outcomes in a resource limited setting?

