1.3.2 Primary Objectives

- To measure how the diversity and relative abundance of the nasopharyngeal resistome of children hospitalised with pneumonia differs from the nasopharyngeal resistome of healthy children in the community.
- To measure how the diversity and relative abundance of the nasopharyngeal resistome of children hospitalised with pneumonia differs from the nasopharyngeal resistome of children with pneumonia treated with antibiotics in the community.
- Investigate whether there is measurable persistence of a hospital-acquired nasopharyngeal
 resistome post-discharge, and whether this is associated with adverse health outcomes,
 including recurrent hospitalisation.

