2.0 Methodology

2.1 Study design

This is a multi-site, extended case-control study with a preliminary cohort component to assess the evolution of the NPR under selective pressure of antibiotic use and hospital admission for pneumonia in children aged 12-24 months in Malawi. The study will be led by the PhD student, [name], as a PhD fellowship.

NP Resistome Study

Version 5.0 21/05/2025

Page 10 of 30

In the preliminary cohort component, healthy children in the community will have a NPS collected at the first study visit, to determine the baseline community resistome through metagenomic sequencing (see Figure 1).

To assess the impact of oral antibiotics on the NPR, children presenting with pneumonia to community healthcare clinics, Ndirande and Gateway Primary Care Centre (GPCC), will have a NPS collected at the first study visit and 3-months post-recruitment, to determine the antibiotic-exposed resistome through metagenomic sequencing (see Figure 1).

To understand the impact of broad-spectrum intravenous antibiotics and exposure to a hospital environment on the NPR, children hospitalised with pneumonia (without any hospital admission 6 months prior) to Queen Elizabeth Central Hospital (QECH) will have a NPS collected at the first study visit, discharge and 3-months post-recruitment to determine a hospital-acquired resistome through metagenomic sequencing (see Figure 1).

[figure not shown]

Figure 1. Preliminary cohort component of the study. The yellow diamonds represent the key samples groups for NPR comparison.

The case-control component of the study will examine whether a hospital acquired NPR is associated with adverse health outcomes, specifically re-admission to hospital with pneumonia. Children hospitalised to QECH with pneumonia (without admission 6 months prior), who are not re-admitted within 3 months will form the control group (see Figure 2); these participants will have a NPS will be collected at the first study visit (within 24 hours of admission to hospital), discharge from hospital and 3-months post-recruitment to assess for a hospital-acquired resistome. Those hospitalised within the preceding 6 months will be

NP Resistome Study

Version 5.0 21/05/2025

Page 11 of 30

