2.5 Sample size and calculations

There is no established method for sample size calculation in resistome studies; we use an approach for microbiome studies [25]. Differences in gut plasmidome composition have been detected with 41 participants per group [26], but NPR has a lower biomass than gut resistome, therefore the resistome is likely to be less diverse, with a lower relative abundance of ARGs. NPR analysis 3.5 years post-antibiotic exposure in a cluster-randomised trial of mass-azithromycin administration shows a trend toward decreased NPR diversity (p = 0.07) in azithromycin clusters when compared to placebo clusters, with just 25 samples per group (unpublished data).

We have used the measured difference in relative abundance of a specific macrolide ARG (ermX) 3.5 years after mass-azithromycin administration (unpublished data) as a medium effect size that maybe clinically relevant (Δ = 0.505). Using the approach for microbiome studies, accepting 90% power and 5% type I error (95% confidence interval),

NP Resistome Study

Version 5.0 21/05/2025

Page 15 of 30

we've calculated that we will require a sample size of 83 participants in each group to detect this effect size, using the formula $n=2(Z_{1-\alpha/2}+Z_{1-\beta})^2/\Delta^2$ [25].

In total we aim to recruit 350 study participants: 83 healthy community participants, 92 participants with pneumonia in the community, 92 participants admitted to hospital with pneumonia and 83 participants re-admitted to hospital with pneumonia. Study groups with a sample size of 92 participants permit a 10% loss to follow up.

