2.9 Statistical analysis

The statistical analysis plan is briefly summarised below. A detailed statistical analysis plan will be developed prior to starting recruitment.

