2.9.1 Primary analysis

Participants will be gender-matched across groups. To establish differences in NPR composition the mean NPR diversity in a sample (measured using the Shannon index), mean relative abundance of all ARGs in a sample and mean relative abundance of specific ARGs in a sample will be compared between study groups using unadjusted t-tests, as summarised in Figure 4. Statistical analysis will be performed in R. Results will be presented in tables and illustrative heatmaps.

[figure not shown]

Figure 4. Plan for statistical analysis of NPR composition.

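### PCA and NMDS are given the job of deciding whether a distinct hospital-acquired resistome exists, but they can only display separation, not test it

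*Protocol*

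**What the plan says.** The broad objective (Protocol 1.3.1) is "To determine whether hospital admission and antibiotic treatment for pneumonia generate a persistent hospital-acquired nasopharyngeal resistome in Malawian children", and whether this is linked to adverse outcomes. The third primary objective (1.3.2) begins "Investigate whether there is measurable persistence of a hospital-acquired nasopharyngeal" resistome after discharge. Both presuppose that such a resistome can be shown to exist.

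Section 2.9.2 assigns that question to ordination: "Principal component analyses and non-metric multidimensional scaling will be used to determine whether there is a distinct hospital-acquired NPR in hospitalised participants". It names no accompanying test or criterion. The next sentence of the same section does name a model, conditional logistic regression, for the association with re-hospitalisation.

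The primary analysis (2.9.1) takes the mean Shannon index, the mean relative abundance of all ARGs and the mean relative abundance of specific ARGs. These "will be compared between study groups using unadjusted t-tests, as summarised in Figure 4". Figure 4 is not reproduced in the text available.

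On sampling (2.1), hospitalised children "will have a NPS collected at the first study visit, discharge and 3-months post-recruitment to determine a hospital-acquired resistome through metagenomic sequencing", and children with pneumonia in the community "will have a NPS collected at the first study visit and 3-months post-recruitment, to determine the antibiotic-exposed resistome through metagenomic sequencing". Section 2.9 calls itself a brief summary and adds: "A detailed statistical analysis plan will be developed prior to starting recruitment".

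**The concern.** Ordination reduces many variables to a few axes so that samples can be looked at. Whether two clouds of points appear separate depends on the distance, the axes kept and the reader. Nothing in the output says how often an equal separation would arise by chance. If no separation is seen, nothing bounds the size of difference that may have been missed.

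If section 2.9.2 is followed as written, the existence of a distinct hospital-acquired resistome would rest on a visual reading. Persistence after discharge would then be interpreted on top of it. The design makes such a reading harder. Section 2.4 reports seasonal variation in the nasopharyngeal microbiome and resistome, and community participants are recruited before hospital participants. Clusters on a plot could partly reflect calendar time.

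**Working it through.** **1. The protocol's own figure and what it covers.** Inputs from section 2.5: effect size 0.505, two-sided alpha 5%, power 90%.

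- n = 2(z₀.₉₇₅ + z₀.₉₀)² / Δ² = 2(1.960 + 1.282)² / 0.505² = 82.4, rounded up to 83 per group. This reproduces.
- Power at 83 per group is 90.2%.
- Loss to follow-up: 92 × 0.9 = 82.8, about 83. Total: 83 + 92 + 92 + 83 = 350.

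The formula is for a difference between two means, so it supports the t-tests in 2.9.1. No quantity in it corresponds to a PCA score plot or an NMDS configuration, and the protocol gives no error rate or power for that step.

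**2. Do the t-tests answer the question instead?** The Shannon index is H = −Σ pᵢ ln pᵢ and total abundance is Σ aᵢ. Both sums are unchanged if the gene labels are exchanged. Two groups can therefore have equal H and equal total abundance while carrying entirely different ARGs. The tests on specific ARGs can detect a shift in a single gene, but they do not yield one conclusion on whether overall composition differs.

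**3. Why a replacement test must respect the child.** The protocol gives no within-child correlation ρ, so a range is assumed. Section 2.1 gives three swabs per hospitalised child and two per child with community pneumonia.

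- *Between groups.* The set-up was 83 children per group, 3 and 2 swabs each, 10 features, no true difference and 500 simulated data sets. A distance-based permutation test that pooled all swabs rejected at a nominal 5% in these proportions:

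| ρ (assumed) | Type I error |
|---|---|
| 0 | 5.8% |
| 0.3 | 21.6% |
| 0.5 | 35.0% |
| 0.7 | 50.8% |

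- *Admission versus discharge in the same child.* Ignoring the pairing errs the other way. Type I error = 2[1 − Φ(1.96/√(1−ρ))], which is 1.9% at ρ = 0.3 and 0.6% at ρ = 0.5.

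The protocol proposes neither of these analyses. The figures show only that the permutation scheme has to be written down once a test is named.

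**4. Precision of a direct persistence measure.** If about 83 hospitalised children supply all three swabs, a proportion near 0.5 (the widest case) has a 95% half-width of 1.96 × √(0.25/83) = 0.108, about 11 percentage points. The planned sample supports a usable estimate.

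**The case against.** The strongest reply is that the protocol does test resistome differences. Section 1.1 describes resistome composition as ARG abundance and diversity. On that definition the primary t-tests address composition, with a stated alpha and power, and the ordination is labelled secondary. This stands in part. A reader might infer that ordination is the only analysis bearing on the objective, and the document does not support that. What has no test is overall distinctness, the specific question that 2.9.2 gives to PCA and NMDS.

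A second reply is that a detailed analysis plan is promised, and that distance, permutation count and covariates belong there. This is right for those details. It does not dispose of the point, because 2.9.2 already commits to methods that cannot answer the question set for them, and an analysis plan that expanded it faithfully would inherit the problem.

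Three further readings are tempting but go beyond the text:

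- **Repeat swabs plotted as if independent.** Section 2.9.2 does not say which swabs enter the ordination. The caption of Figure 1 refers to key sample groups for comparison, and Figures 1 and 4 cannot be seen.
- **PCA run on raw relative abundances.** No input scale, transformation or distance is stated.
- **Standard errors about 30% too small.** With three swabs and an assumed ρ of 0.5 the variance factor is 1 + 2 × 0.5 = 2.0, and 1/√2 = 0.71. That describes a test of group centroids the protocol does not propose. For admission versus discharge the error would be conservative.

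**Conclusion.** The point holds in a limited form. Section 2.9.2 assigns a yes/no question, on which the broad objective and the third primary objective depend, to methods that give no test, interval or error rate. The t-tests cover related summaries but not overall composition, and the 5% alpha and 90% power of section 2.5 do not extend to the ordination.

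No bias can be put in figures, because the protocol states no inferential procedure for this step. The conclusion rests on the wording of 2.9.1 and 2.9.2 and on what PCA and NMDS return; it needs no assumption about correlation. It is of moderate weight: the analysis is labelled secondary, but the objectives that rely on it are not.

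**What to change.** - Reword 2.9.2 so that PCA and NMDS describe and illustrate. Base the conclusion on a named multivariate test at a stated alpha, for example PERMANOVA on Aitchison or Bray-Curtis distance, reporting R².
- Add a test of dispersion. PERMANOVA also responds to unequal spread, and the hypothesis in 1.2 predicts a less diverse resistome after antibiotics, so unequal spread is plausible.
- Permute within child for the admission, discharge and 3-month contrasts. For between-group contrasts use one swab per child or permute whole children.
- Report the proportion of hospitalised children, with a 95% CI, who have ARGs absent at admission, present at discharge and still present at 3 months. Set the detection threshold beforehand, because a low-biomass swab can miss a gene that is there.
- Adjust for age and prior antibiotics, both already recorded (2.1). Adjust for calendar time only where groups overlap in time, which is mainly healthy community versus hospital: under 2.4 only healthy children continue to be sampled over the following 6 months. State that season cannot be reliably separated from group for community pneumonia versus hospital.

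The cost is changed wording and a little more analysis in R, which 2.9.1 already names. The swabs are already planned and no new data are needed.

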Age, gender, co-morbidities, mid-upper arm circumference, pneumococcal vaccination status, antibiotics received 7 days prior to recruitment, haemoglobin level and malaria screening results will be recorded for all participants at recruitment; exposure to tobacco smoke from a household contact and whether the participant was breastfed in their first 3 months of life will also be recorded, as these are independently associated with pneumonia requiring hospitalisation in high-income settings [21]. Mode of childbirth (vaginal versus caesarean section) will also be recorded, as this influences early NPM development, and may be associated with childhood respiratory health [22]. To assess for acquisition of MGEs from the hospital environment, we will record data on duration of hospitalization and incidence of shared bed-spaces for hospitalised study participants, including number of occupants and number of days in a shared bed-space. Shared hospital bed-spaces will be sampled using a swab for metagenomic sequencing. Groups undergoing repeat NPS at 3 months will have health outcomes (including mortality), healthcare interactions (including healthcare facility and hospital attendance/admission) and antibiotic exposure recorded.

Groups being admitted to hospital will have WHO markers of severity in pneumonia recorded, including presence of the following at the time of admission: central cyanosis, oxygen saturations less than 90%, inability to feed, vomiting, convulsions, lethargy and impaired consciousness. To assess for potential influence of healthcare seeking behaviour on hospital re-admission, groups presenting to healthcare clinics and/or hospitals with pneumonia will have the educational level of the parents recorded, and the distance travelled to the healthcare clinic.

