2.15.1 Failure to recruit sufficient participant numbers

A major potential challenge to study completion is identifying enough participants being re-hospitalised within 3 months to meet our recruitment targets. There is no data on hospital re-admission rates due to pneumonia in Sub-Saharan Africa. The leading cause of recurrent hospitalisation among children aged under 5 years in Sub-Saharan Africa is severe anaemia, with a readmission rate of 18% over 6 months [27]. A study conducted at QECH between April 2013 and August 2016 recruited 1600 children presenting with pneumonia that met the WHO's Integrated Management of Childhood Illness (IMCI) definition: cough or

NP Resistome Study

Version 5.0 21/05/2025

Page 23 of 30

difficult/fast breathing [30]; this is broader than our clinical definition, but based on this we could expect to recruit approximately 500 children hospitalised with pneumonia in a 12-month period. If the hospital re-admission rate were equal to severe anaemia at 18% over 6 months, this would equate to just 90 cases in a 12-month period.

A 4-week audit of hospital re-admission rates of children aged 12-24 months with pneumonia will be conducted at QECH before starting study recruitment, to further inform sample size calculations. We will use parent/carer reporting and patients' health passports as screening tools to identify those being re-admitted within 3 months of a previous hospitalisation with pneumonia. Our budget includes a stipend for hospital nursing staff to identify potentially eligible patients for screening during the admission process.

If the study experiences low participant enrolment numbers within the first 4 months, we will reassess and renew our CEI activities. Potential adjustments to the study design could include a wider age-range of study participants, although this would likely result in greater variability of baseline NPM and NPR; modifying the case to control ratio to 0.75 to 2; or adjusting the case definition to include hospital re-admissions with any infection requiring antibiotics within 3 months of hospitalisation with pneumonia, which may enable us to capture the extra-pulmonary adverse health effects of AMR.

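### In the re-hospitalisation regression, severity and probably length of stay refer to the index admission in controls but to the outcome admission in cases; antibiotics after the first admission are captured unequally; and no matched sets are defined beyond gender

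*Protocol*

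**What the plan says.** Section 2.9.2 states: "Conditional logistic regression will be used to test for association between NPR composition and re-hospitalisation with pneumonia within a 3-month period". The confounders it names are "co-morbidities, nutritional status, duration of hospital admission and severity of pneumonia", given as examples rather than a closed list. It does not say which admission is meant. The only matching is in section 2.9.1: "Participants will be gender-matched across groups".

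Section 2.1 defines the groups. Children admitted with pneumonia, with no admission in the previous 6 months, "who are not re-admitted within 3 months will form the control group"; they are swabbed at admission, at discharge and at 3 months. Cases are enrolled at a re-admission within 3 months of an earlier pneumonia admission, and have one swab, within 24 hours of that re-admission. Section 2.7.3.7 allows the earlier admission to have been at any hospital.

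For data capture, section 2.1 records severity markers as present on admission, duration of stay for hospitalised participants, and, for everyone, "antibiotics received 7 days prior to recruitment". Later antibiotic exposure is tied to the repeat swab: "Groups undergoing repeat NPS at 3 months will have health outcomes (including mortality), healthcare interactions" and antibiotic exposure recorded. Section 2.5 sets the group sizes: "92 participants admitted to hospital with pneumonia and 83 participants re-admitted to hospital with pneumonia". A case-to-control ratio appears only as a contingency in section 2.15.1: "modifying the case to control ratio to 0.75 to 2".

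**The concern.** This is the only adjusted analysis described for the link between resistome and re-admission, which is part of the third primary objective (section 1.3.2). A confounder must be measured on the same footing in cases and controls and must not follow from the outcome. If severity and duration come from the first admission in one group and from the outcome admission in the other, adjusting for them partly adjusts for being a case.

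Antibiotic selection is the study's own hypothesis (section 1.2), and section 1.1 aims to separate its effect from that of admission. Antibiotics taken between discharge and re-admission are an obvious alternative explanation for a more resistant resistome in cases. A later statistical analysis plan can add a variable to a model, but it cannot recover data that were never collected.

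**Working it through.** **1. The plan's own figure.** Section 2.5: n = 2(Z₀.₉₇₅ + Z₀.₉₀)²/Δ² = 2(1.960 + 1.282)²/0.505² = 82.4, rounded up to 83 per group; power at 83 is 0.902. With 10% loss, 92 × 0.9 = 82.8. The figure reproduces. It sizes a comparison of two means, not this regression, and is not in dispute.

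**2. What each covariate describes, following section 2.1.**

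| Item | Controls | Cases |
|---|---|---|
| Admission at enrolment | First (index) | Re-admission (the outcome) |
| Severity | Index admission | Re-admission |
| Duration of stay | Index admission | Re-admission, by inference |
| Length or severity of the earlier stay | Not applicable | No item listed |
| Antibiotics, 7 days before recruitment | Recorded | Recorded |
| Antibiotics after the first admission | Followed to 3 months | Only the last 7 days before re-admission |

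Severity is explicit, because the markers are those present at the study admission. Duration is an inference, because section 2.9.2 does not name the admission. If it means the recorded stay, then in cases it accrues after both the outcome and the swab and cannot confound their association. The health passport and carer report are used to establish that an earlier admission occurred; no length or severity item is attached to that step.

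**3. Other sources of antibiotic data.** The urine sample is taken at the first visit (sections 2.1 and 2.15.6) and cannot reconstruct weeks of earlier exposure. The record card and drug-bag aid in section 2.15.6 are not described as covering the time before a case is enrolled.

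**4. Conditioning sets.** No section links a case to particular controls, and the groups are recruited to separate totals. Conditional regression could use two gender strata, or someone could form same-sex pairs after the event. To see whether pairing matters, data were simulated under these assumptions: 83 cases, 83 controls, matching on sex only, a standardised difference of 0.505 and four covariates with no effect.

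- Over 1,000 runs, power was 0.90 for unconditional regression with a sex term and 0.89 for conditional regression on arbitrary same-sex pairs.
- In each of three single data sets, 200 arbitrary pairings gave these ranges:

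| Data set | Unconditional p | p over pairings | Unconditional log-odds | Log-odds over pairings |
|---|---|---|---|---|
| 1 | 0.034 | 0.009 to 0.109 | 0.35 | 0.25 to 0.56 |
| 2 | 0.00001 | 0.00003 to 0.0006 | 0.81 | 0.61 to 1.36 |
| 3 | 0.095 | 0.040 to 0.279 | 0.26 | 0.17 to 0.36 |

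Average power hardly changes. In two of the three data sets, the choice of pairs decides which side of 0.05 the result falls.

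**The case against.** The strongest defence has four parts.

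- **Matching.** Gender matching is stated, and naming strata is ordinary content for the analysis plan that section 2.9 defers to. A reader might infer that the regression has nothing to condition on. The protocol does not support that: two gender strata are available. What stands is that nothing finer is defined, and matching not done at recruitment cannot be created later.
- **Antibiotic windows.** A reader might infer 7 days of capture in cases against 3 months in controls for the same period. That is not what the protocol says. The 7-day look-back is the same for everyone, and if a case's swab is compared with a control's admission swab the windows agree. The figures that may fix this comparison are not shown. The imbalance concerns the interval after the first admission, which matters when the control's 3-month swab is the comparator.
- **Open confounder list.** Antibiotics are not named, but they are not excluded. This is fair. The difficulty is that no comparable post-discharge variable is described for cases.
- **Duration.** In a model of re-hospitalisation the preceding stay is a natural reading, and the case report form is not shown. This is also fair, and it is why duration is treated as an inference. Even on that reading, no listed item supplies the preceding stay for cases. The severity point does not depend on it.

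**Conclusion.** The point holds in three parts. Severity explicitly, and duration by inference, are on different footings in cases and controls. Antibiotics after the first admission are captured unequally. The conditioning sets are undefined beyond gender. The first two rest on the items listed in section 2.1 and assume that the case report form adds nothing to them.

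The documents give no basis for sizing the bias in the odds ratio. A reader might take 7/90 = 8% as the share of post-discharge courses captured in cases and conclude that the antibiotic effect would be reversed. That does not follow. Cases return within 3 months, so the interval is shorter (at an assumed 45 days, 7/45 = 16%). Courses are unlikely to be evenly spread either, since section 1.1 says antibiotic use before seeking care is common. Any distortion of an antibiotic effect also presupposes that antibiotics enter the model. Unequal capture is established; its direction and size are not.

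For the conditioning sets, the harm is an arbitrary result rather than lost power (0.89 against 0.90), under the simulation assumptions given. This should be changed before case recruitment, because the missing items cannot be recovered reliably afterwards.

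**What to change.** Reconcile sections 2.1, 2.9.1 and 2.9.2 as follows.

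1. At case enrolment, record from the health passport and carer, with the drug-bag aid already planned: index admission and discharge dates, hospital, length of stay, any available severity markers, and antibiotic courses between index discharge and re-admission. Keep the 7-day item.
2. State in section 2.9.2 that duration and severity mean the index admission in both groups. Remove re-admission duration and severity from the main model.
3. State which control swab enters the model. When it is the 3-month swab, name post-discharge antibiotic exposure as a confounder, defined the same way in both groups and excluding in-hospital treatment during the index stay.
4. Use unconditional logistic regression with a sex term, or condition on gender strata only. Do not form arbitrary pairs.

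Two variables that may suggest themselves should stay out. Days since index discharge nearly separates the groups by design. Any antibiotic use in the past 3 months may hardly vary in controls, all of whom were prescribed antibiotics at the index admission as an inclusion criterion.

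The cost is a few form fields and some redrafting. Recall over weeks is less accurate than over 7 days, and index severity from another hospital will sometimes be missing.
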